The likelihood ratio of a positive and a negative result for ultrasonography were 10.74 and 0.03 respectively, and that for capnography were infinity and 0.04 respectively.

The kappa value was 0.749 (95% CI: 0.567 – 0.931) which meant a good degree of agreement of result between these two methods.

The average time taken for confirmation of endotracheal tube by ultrasonography and capnography were 26.79 ± 7.64 seconds and 43.03 ± 8.71 seconds (mean \pm standard deviation) respectively. The median time for confirmation was 26 seconds with interquartile range [15 - 37] seconds for ultrasonography and 42 seconds with interquartile range [29 - 55] seconds for capnography. Ultrasonography was found to be faster than capnography by 16.36 ± 3.23 seconds (mean \pm standard deviation) and the difference in time was significant ($p = 0.011$).

Conclusion:

Ultrasonography and waveform capnography are both reliable and accurate methods of confirming endotracheal tube position. The use of ultrasound with capnography will help reduce time and increase precision of confirming endotracheal tube position. Ultrasound can confirm endotracheal tube position before manual bag ventilations, and thus may prevent aspiration of gastric contents into patient's lungs.

Keywords: Endotracheal intubation; ultrasonography; capnography.

TABLE OF CONTENTS

Serial No.	Contents	Page No.
1	Introduction	7
2	Literature Review	19
3	Objectives	30
4	Hypothesis	31
5	Methodology	32
6	Results	45
7	Discussion	55
8	Limitations	68
9	Conclusion	69
10	Recommendations	70
11	References	71
12	Appendices	
	Appendix A - PAC Form	77
	Appendix B - Consent	79
	Appendix B – Proforma	80
	Appendix D – Thesis approval letter from IRB	82

LIST OF ABBREVIATIONS

%	Percentage
>	Greater than
<	Lesser than
±	Plus– Minus
α	Alpha
ACLS	Advanced Cardiac Life Support
AHA	American Heart Association
ASA	American Society of Anesthesiologists
β	Beta
BMI	Body Mass Index
BPM	Beats Per Minute
CI	Confidence Interval
CL	Cormack Lange
CO ₂	Carbon Dioxide
COPD	Chronic Obstructive Pulmonary Disease
CPR	Cardiopulmonary Resuscitation
DLT	Double-Lumen Tube
ECG	Electrocardiogram
Eg	Example
ET	Endotracheal
ETCO ₂	End Tidal CO ₂
NIBP	Non-Invasive Blood Pressure
IRB	Institutional Review Board

IOM	Institute of Medicine
IQR	Interquartile Range
κ	Kappa value
Kg	kilogram
LMA	Laryngeal Mask Airway
LR ⁺	Likelihood ratio of a positive test
LR ⁻	Likelihood ratio of a negative test
MCVTC	Manmohan Cardiothoracic Vascular and Transplant Center

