Both ultrasonography and waveform capnography were found to be good, reliable and fairly accurate diagnostic methods of confirming endotracheal tube position. Ultrasonography was comparable diagnostically with capnography for endotracheal tube confirmation. The comparisons of the pretest and posttest probabilities of the two methods are shown in table 10.

Table 10. Comparison of the diagnostic characteristics of ultrasonography and waveform capnography.

	Ultrasonography	Waveform Capnography
Sensitivity in % (95% CI)	97.62 (91.66- 99.71)	96.43 (89.92 - 99.26)
Specificity in % (95% CI)	90.91 (58.72 - 99.77)	100 (71.51 - 100)
PPV in % (95% CI)	98.80 (92.67- 99.81)	100 (100 – 100)
NPV in % (95% CI)	83.33 (55.66 - 95.22)	78.57 (54.69 - 91.76)
Accuracy in % (95% CI)	96.84 (92.92 - 100)	96.84 (92.92 - 100)
Positive likelihood ratio	10.74	Infinity
Negative likelihood ratio	0.03	0.04

(CI= Confidence Interval, PPV= Positive Predictive Value, NPV= Negative Predictive Value)

Both ultrasonography and capnography together had correctly identified 10 out of the 11 oesophageal intubations. The 84 tracheal intubations were correctly identified by both ultrasonography and capnography or either one of these methods. Using the same formula (page 35), the combined accuracy of both the methods together was 98.94% (94 divided by 95, in percentage).

The analysis of agreement between the ultrasonography and capnography results was done using Cohen's kappa statistics. A kappa value of 0.749 with 95% confidence interval of (0.567 – 0.931) and standard error of 0.093 was found. The kappa value therefore showed a good agreement between the result of these two methods.

Time taken for endotracheal tube confirmation

Real-time ultrasonography was faster than waveform capnography for endotracheal tube confirmation in all cases. The mean time for confirmation by ultrasonography was 26.79 ± 7.64 seconds (mean \pm standard deviation). The mean time for confirmation by capnography was 43.03 ± 8.71 seconds.

The mean difference in time was 16.36 seconds (95% CI: 15.70sec – 17.02 sec). The median difference in time was 16 seconds. The standard deviation in difference in time was 3.23 seconds. The standard error of mean (SEM) was 0.332 seconds. The difference in time was highly significant ($p = 0.011$).

Table 11. Time taken for endotracheal tube confirmation.

	Range (in seconds)	Mean \pm SD (in seconds)	Median (in seconds)	IQR (in seconds)	p-value

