Time taken by ultrasonography	14 - 50	26.79 ± 7.64	26.00	[15 - 37]	
Time taken by capnography	27 - 67	43.03 ± 8.71	42.00	[29 - 55]	
Difference in time (ultrasonography - capnography)	9 - 24	16.36 ± 3.23	16.00		0.011

(SD = Standard Deviation, IQR = Inter-Quartile Range, Range = Maximum-minimum values)

A subgroup analysis was done to test whether the time delay in sidestream capnograph could have affected the p-value obtained in difference in time. Two subgroups were divided: one subgroup in which sidestream capnography was used, and the other subgroup in which mainstream capnography was used. There were 37 patients in the mainstream subgroup and 58 patients in the sidestream subgroup. The median time for confirmation of endotracheal tube position in mainstream subgroup was 37 seconds. The median time for confirmation of endotracheal tube position for

capnography in sidestream subgroup was 45.5 seconds. The findings of difference in time between ultrasonography and capnography methods in these subgroups are summarized in table 12.

Table 12. Subgroup analysis for difference in time taken for endotracheal tube confirmation.

Difference in time (ultrasonography-capnography)	Range (in seconds)	Mean \pm SD (in seconds)	Median (in seconds)	p-value
Mainstream subgroup (n=37)	9 - 19	14 \pm 2.62	14	p < 0.01
Sidestream subgroup (n=58)	12 - 24	17.87 \pm 2.64	17.50	p < 0.01

(SD = Standard Deviation, Range = Maximum - minimum values)

The distribution was found to be normal in both subgroups on applying Shapiro-Wilk test (p < 0.01). Student's t- test was used to determine the p-value of difference in time to confirm endotracheal tube position between the two subgroups. The p-value, p < 0.01 was obtained in both the subgroups, which meant that use of sidestream capnography with a delay time did not affect the significant difference in time between ultrasonography and capnography found in this study.

DISCUSSION

Both ultrasonography and waveform capnography were found to be reliable and accurate methods of confirming endotracheal tube position in this study. The variables that were studied and analyzed in this study are now discussed further.

Descriptive data

The results of this study were not affected by the demographic and physical health profiles of the subjects.

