This study used both sidestream and mainstream capnographs. This was because of availability of different types of capnograph at the study sites. The details of sampling line delay are discussed later.

Ultrasonography vs Capnography

Both ultrasonography and waveform capnography were found to be good, reliable and fairly accurate diagnostic methods of confirming endotracheal tube position. Though ultrasonography and capnography were equally sensitive and capnography seemed more specific; the sensitivity, specificity, PPV, NPV of ultrasonography were comparable (statistically not different as seen by their confidence intervals) to waveform capnography.

The combination of ultrasonography and capnography increased precision (accuracy) over using either one of them in this study. Since the studies done previously had compared ultrasonography against capnography as the standard and thus calculated the sensitivity, specificity, PPV, NPV of ultrasound; these were not able to show if ultrasound had increased accuracy over using capnography alone.

Both of these methods are now known to be equally reliable. Hence in case of unmatched result given by these two methods in a patient, a third highly reliable method of confirmation has to be used because both ultrasonography and capnography have statistically not different false positive (1 – specificity) and false negative (1 – sensitivity) rates.

There was generally good agreement between the results produced by ultrasonography and capnography as shown by the kappa value of 0.749 with 95% confidence interval of (0.567 – 0.931). Other studies have shown a good or a very good agreement of these two methods by kappa statistics. The kappa value calculated by Adi et al³⁰, Chou et al²⁸, Karacebay et al²⁷ and Chintamani et al³⁴ were 0.85, 0.93 (0.84 – 1.00), 0.85 and 0.76 respectively.

Real-time, transtracheal, transverse suprasternal ultrasonography was significantly faster ($p = 0.011$) than capnography by 16.36 ± 3.23 seconds (mean \pm SD) in confirming endotracheal tube position in this study. The subgroup analysis between mainstream and sidestream capnographs also showed that the type of waveform capnograph device used did not affect the significant difference in time of ultrasound over capnograph in confirming endotracheal tube position.

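### The time p-value, at least one method mean and the kappa contradict the report's own figures; two Table 10 intervals are faulty, and the capnography IQR is not the quartiles

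*Combined protocol and SAP*

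**What the plan says.** **Time.** Results (Time taken for endotracheal tube confirmation) gives a mean paired difference of 16.36 s, 95% CI 15.70 to 17.02, SD 3.23, and continues "The standard error of mean (SEM) was 0.332 seconds. The difference in time was highly significant", with p = 0.011. It also says "Real-time ultrasonography was faster than waveform capnography for endotracheal tube confirmation in all cases". In Table 11 the row headed "Difference in time (ultrasonography - capnography" has a range of 9 to 24 s and p = 0.011. The method means are 26.79 (SD 7.64) s and 43.03 (SD 8.71) s; the medians are 26 [15 - 37] and 42 [29 - 55]. The abstract repeats that "the difference in time was significant ($p = 0.011"; the Discussion says ultrasound "was significantly faster ($p = 0.011$) than capnography by 16.36" s. For Table 12, "There were 37 patients in the mainstream subgroup and 58 patients in the sidestream subgroup", with mean differences of 14 (SD 2.62) and 17.87 (SD 2.64) s.

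**Agreement.** Results: "A kappa value of 0.749 with 95% confidence interval of" 0.567 to 0.931, standard error 0.093. The abstract agrees: "The kappa value was 0.749 (95% CI" 0.567 to 0.931).

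**Accuracy measures.** Table 10 gives capnography PPV 100 (100 - 100)% and accuracy 96.84 (92.92 - 100)% for both methods. Operational Definitions names Clopper-Pearson intervals and then prints an estimate ± 1.96 SE formula.

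**Software.** Statistical Analysis assigns the time statistics, the paired t-test and kappa to SPSS, and the accuracy measures to Excel.

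**The concern.** A paired mean difference about 49 times its standard error cannot have p = 0.011. In paired data the mean difference must equal the difference of the means, and here it does not. Kappa is determined by counts the report itself gives, and the printed value does not follow from them. An interval of 100 to 100% from 81 patients claims certainty. An upper limit of 100% for accuracy is impossible after three observed errors.

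The p-value tests the speed hypothesis, and kappa is specific objective 5. Both are in the abstract and Discussion, where readers and later meta-analyses will take them. The mismatch in means could be a slip in transcription or a sign that the summaries rest on different patients; the text does not show which.

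**Working it through.** **1. p-value.** Inputs: mean difference 16.36, SD 3.23, n = 95.
- The report's SEM and interval reproduce: 3.23/√95 = 0.331 (printed 0.332); 16.36 ± 1.986 × 0.332 = 15.70 to 17.02.
- t = 16.36/(3.23/√95) = 49.4 on 94 df, p = 5e-69 (49.3 and 6e-69 with SEM 0.332).
- p = 0.011 needs |t| = 2.59, a mean difference of 2.59 × 0.332 = 0.86 s.
- The SD is not needed. For 95 values between 9 and 24 s, t is smallest with 26 at 24 s and 69 at 9 s: mean 13.11, SD 6.72, SEM 0.690, t = 19.0, p = 6e-34.
- Other tests do not give 0.011 either: unpaired t 6e-30, sign test 5e-29, between-subgroup t 4e-10, paired tests within subgroups 3e-28 (t = 32.5) and 2e-49 (t = 51.6).

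**2. Means.** 43.03 - 26.79 = 16.24.
- The report sometimes truncates (11/95 = 11.578% is printed as 11.57%). Allowing rounding or truncation, the means support 43.025 - 26.80 = 16.225 to 43.04 - 26.785 = 16.255. The stated difference covers 16.355 to 16.370. The ranges do not meet.
- Table 12 pooled: (37 × 14 + 58 × 17.87)/95 = 16.363. Sum of squares 36 × 2.62² + 57 × 2.64² + 37 × (14 - 16.363)² + 58 × (17.87 - 16.363)² = 982.7, so SD = √(982.7/94) = 3.233.
- Table 12 therefore supports 16.36 and 3.23, and at least one method mean is wrong or rests on other patients.

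**3. Kappa.** The printed interval follows from the printed estimate: 0.749 ± 1.96 × 0.093 = 0.567 to 0.931. The estimate does not follow from the counts.
- Oesophageal cases (11): capnography had no false positive and ultrasound had one, so 10 are negative on both and 1 is tracheal on ultrasound only.
- Tracheal cases (84): the Results say each was identified by at least one method, so no false negative is shared. That gives 2 ultrasound-only misses, 3 capnography-only misses and 79 tracheal on both.
- The printed combined accuracy of 94/95 = (84 + 10)/95 confirms this.

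| | Capnography trachea | Capnography oesophagus | Total |
|---|---|---|---|
| Ultrasound trachea | 79 | 4 | 83 |
| Ultrasound oesophagus | 2 | 10 | 12 |
| Total | 81 | 14 | 95 |

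- Observed agreement 89/95 = 0.9368; chance agreement (83 × 81 + 12 × 14)/95² = 0.7635; kappa = (0.9368 - 0.7635)/(1 - 0.7635) = 0.733.
- Asymptotic SE 0.103, 95% CI 0.531 to 0.935.
- With these margins, 9, 10 or 11 joint negatives give 0.644, 0.733 or 0.822, so 0.749 cannot occur.
- Of all two-by-two tables of 95, the 42 whose kappa rounds to 0.749 have SE 0.097 to 0.098 or at most 0.082, never 0.093. No table of any size from 86 to 110 gives the pair, which covers the 103 enrolled.

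**4. Table 10 intervals.**
- Clopper-Pearson reproduces the sensitivity and specificity intervals of both methods.
- Capnography PPV, 81/81: the ± 1.96 SE formula has SE 0, hence 100 to 100. The Clopper-Pearson lower limit is 0.025^(1/81) = 95.55%. The same table gives the 100% specificity a proper interval, 71.51 to 100%.
- Accuracy, 92/95: SE = √(0.9684 × 0.0316/95) = 0.0179. Rounded to 0.02, 96.84 - 3.92 = 92.92, and the upper value 100.76 is capped. Clopper-Pearson gives 91.05 to 99.34%.
- Ultrasound PPV (92.67 - 99.81) and both NPVs (55.66 - 95.22; 54.69 - 91.76) are reproduced by the logit interval for predictive values built from the sensitivity and specificity variances. The report never names it.

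**5. IQRs.** [29 - 55] is 42 ± 13 and [15 - 37] is 26 ± 11, both exactly symmetric.
- Smallest SD compatible with 29 and 55 as quartiles, holding the printed mean, median and range and allowing at least 23 of 95 values at or beyond each quartile, quartiles ± 1 s and median ± 0.5 s: 8.83 s. With the 24th and 72nd ordered values and no rounding: 9.71 s. Stated SD: 8.71 s.
- The same lenient rule gives 7.42 s for ultrasound, below its stated 7.64 s, so that IQR is not excluded.
- If 13 and 11 s are IQR widths, width/SD is 1.49 and 1.44, close to BMI (5.24/3.58 = 1.46). As printed, the ratios are 2.99 and 2.88.

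**The case against.** The strongest reply is that little depends on these errors. The wrong p-value understates the evidence, and the correct difference, SD, SEM and interval stand beside it. The means are 0.12 s apart against an effect of about 16 s. Kappa moves by 0.016 and stays in the good band, and its lower limit was already in the moderate band as printed. This is true, and it limits the consequence. It does not make the printed values right.

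Four narrower points have some force:
- The Clopper-Pearson sentence follows a list that omits accuracy, so 91.05 to 99.34% is a choice for that row. The unrounded normal interval would be 93.33 to 100.36%, whose upper limit is itself impossible.
- A logit interval is undefined at 81/81, so keeping logit for predictive values would put two methods in the PPV row. Labelling each row would disclose this.
- The capnography SD floor holds the mean at 43.03 s, which may be the wrong mean. With the mean freed, the lenient floor falls to 8.74 s, only 0.03 s above 8.71; with the 24th and 72nd values it is still at least 9.58 s.
- Overlap of intervals is not a valid test for two methods used on the same patients. But the Discussion relies on exactly that reading, and the printed PPV intervals do not overlap, so the text contradicts its own table.

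SPSS being named for all time statistics does not exclude transcription error. It means only that a change of program does not explain the mismatch.

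**Conclusion.** The concern holds. p = 0.011 should be about 5e-69. The method means imply 16.24 s against the stated 16.36 s. Kappa is 0.733 (0.531 to 0.935), not 0.749 (0.567 to 0.931). Capnography PPV should read 95.55 to 100%, and accuracy for both methods 91.05 to 99.34%, under Clopper-Pearson. These must be corrected. The IQRs and the missing method labels should be corrected: the capnography IQR is not the ordinary quartiles, and the ultrasound IQR is only suspect.

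The kappa result assumes that Tables 8 and 9 and the joint-result statements are right. The p-value result needs only the stated range of differences. Which method mean is wrong, and where 0.011 and 0.749 came from, cannot be told without patient-level data. Ultrasound remains faster, kappa remains good, and the sensitivity and specificity intervals are correct.

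**What to change.** - Report p < 0.001 with the interval 15.70 to 17.02 s.
- Check the 95 pairs of times and correct the wrong mean or means.
- Print the ultrasound-by-capnography cross-table and trace the kappa input against Tables 8 and 9. If those tables stand, report 0.733 (0.53 to 0.94).
- Replace the capnography PPV interval with 95.55 to 100% and both accuracy intervals with 91.05 to 99.34%.
- Name the interval method for every row of Table 10. Either declare logit for ultrasound PPV and both NPVs, or use Clopper-Pearson there too (93.47 to 99.97%; 51.59 to 97.91%; 49.20 to 95.34%).
- Report the true 25th and 75th percentiles of both times. If 11 and 13 s are IQR widths, they were printed as median ± width.
- Carry every change into the abstract and Discussion.

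The cost is a re-run of existing data and edits to Tables 10 and 11, the abstract and the Discussion. No new data are needed.

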< 0.1	Large change in likelihood (or in other words high probability of any individual having a negative result on using the diagnostic test).
0.1 – 0.2	Moderate change in likelihood.
0.2 – 0.5	Small change in likelihood.
1	No change.

Data collection and management

The Pre-anaesthetic (PAC) form of the Department of Anaesthesiology, MMC, IOM; (Appendix A) was used to evaluate patients for inclusion into the study. All participants' data such as gender, age, ethnicity, diagnosis, BMI, weight, ASA status, medical comorbidities, airway examination was collected on data entry proforma sheet (Appendix C). The proforma sheet also recorded the baseline vitals and the vitals after induction of anaesthesia and after intubation. The results for ultrasonography and capnography, the respective time taken to obtain the results were recorded in the proforma sheet.

Data entry was done into Microsoft excel 2010. (Appendix E)

Statistical Analysis

Descriptive variables were expressed as mean \pm standard deviation, median, range, interquartile range, frequency, percentage and proportion. The calculations were done in Microsoft excel 2010.

The sensitivity, specificity, positive and negative predictive values, accuracy, along with their confidence intervals and likelihood ratios for positive and negative results were calculated by defining the respective mathematical functions into Microsoft excel 2010.

The mean and median times along with the interquartile range and standard deviations, taken for confirmation by capnography and ultrasonography were calculated using SPSS 23.0. Difference in time was calculated as method 1 (ultrasonography) minus method 2 (capnography) and reported as mean with 95% confidence interval; the results were compared using paired student t-test with p values at 95 % level of significance. The analysis was done using SPSS 23.0.

Kappa statistic was used to see agreement over and above that which would have occurred just by chance between these two methods. The kappa (κ) value was calculated using SPSS 23.0. It was interpreted based on the following criteria³⁸:

Table 4. Interpretation of kappa value.³⁸

Kappa value (κ)	Degree of agreement
0.81 - 1.00	Very good.
0.61 - 0.80	Good.
0.41 - 0.60	Moderate.
0.21 - 0.40	Fair.
<0.20	Poor.

[figure not shown]

Fig. 8. Study flow diagram.

(TP=True Positive, FP=False Positive, TN=True Negative, FN=False Negative)

RESULTS

Descriptive data

Demography

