The sidestream capnograph at MCVTC had system response time of < 4 seconds, and that at TUTH had system response time of < 3 seconds. Adjusting for rise time of 200 milliseconds (the actual rise time of sidestream capnograph device used at TUTH; the rise time of that used at MCVTC was unknown), the transit time (delay time) would be in between 3 to 4 seconds in MCVTC sidestream capnograph and in between 2 to 3 seconds in TUTH sidestream capnograph. No delay was expected in mainstream capnograph device.

The median time taken for endotracheal tube confirmation by mainstream capnograph was 37 seconds and that by sidestream capnograph was 45.5 seconds. The combined median time taken for endotracheal tube confirmation by capnography was 42 seconds. The difference in time with ultrasonography was maximum of 19 seconds and minimum of 9 seconds while using mainstream capnograph, and maximum of 24 seconds and minimum of 12 seconds while using sidestream capnograph. These findings correlate to the delay time of sidestream capnographs as mentioned previously. Though theoretically the delay time should not have exceeded 4 seconds, the difference in median time for confirmation between these types of capnographs was 8.5 seconds. The median time for confirmation of endotracheal tube position in this study would be affected by the time taken by the anaesthesia resident for intubation. Thus difference in time for confirmation between the two types of capnographs could be greater or lesser than 8.5 seconds depending on the variability of time taken for intubation in this study.

Few studies have compared if ultrasound can be faster than capnography. Karacebay et al²⁷ found that dynamic transtracheal ultrasound at suprasternal level combined with lung sliding done by two separate operators simultaneously during intubation, was faster in average by 5.9 seconds than capnography for endotracheal tube confirmation. Pfeiffer et al³¹ found that lung ultrasound was in average 7.1 seconds faster than capnography in confirming endotracheal tube position.

The difference in time was greater in this study, likely due to use of sidestream capnograph. But as discussed earlier, this did not affect the significance in difference in time.

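### The subgroup paragraph reads a Shapiro-Wilk p < 0.01 as normality and gives only within-subgroup p-values for a test it calls between-subgroup; the 3.87 s longer sidestream lead is not reported

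*Combined protocol and SAP*

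**What the plan says.** The Statistical Analysis section plans one comparison of times, for all patients together: "the results were compared using paired student t-test with p values at 95 % level of significance". It lists no subgroup analysis. The Results report the pooled lead: "The mean difference in time was 16.36 seconds", with SD 3.23 s and 95% CI 15.70 to 17.02 s.

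The Results then add a subgroup analysis and state its purpose: "A subgroup analysis was done to test whether the time delay in sidestream capnograph could have affected the p-value obtained in difference in time". Table 12 gives a lead of 14 ± 2.62 s for 37 mainstream patients and 17.87 ± 2.64 s for 58 sidestream patients, each with p < 0.01. Three statements follow:

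- on distribution: "The distribution was found to be normal in both subgroups on applying Shapiro-Wilk test (p < 0.01";
- on the test: "Student's t- test was used to determine the p-value of difference in time to confirm endotracheal tube position between the two subgroups";
- on its meaning, after p < 0.01 is given for each subgroup: "which meant that use of sidestream capnography with a delay time did not affect the significant difference in time between ultrasonography and capnography".

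The Discussion (Ultrasonography vs Capnography) repeats that "the type of waveform capnograph device used did not affect the significant difference in time of ultrasound over capnograph". Later in the same section, when comparing with other studies, it says: "The difference in time was greater in this study, likely due to use of sidestream capnograph". Limitation 1 names the mix of device types and Limitation 2 the use of several ultrasound operators.

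**The concern.** Two statements in the paragraph do not match the figures attached to them. First, normality is the null hypothesis of the Shapiro-Wilk test, so a small p-value is evidence against it. Second, a test between two subgroups yields one p-value, whereas the text and Table 12 give one per subgroup. Two significant within-subgroup results show that ultrasonography was called earlier with each device type. They do not compare the two leads.

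At stake is the size of the lead, not its existence. The Abstract and the Discussion quote 16.36 s without the two subgroup values. A reader who takes the subgroup paragraph to mean that device type made no difference would apply 16.36 s to either kind of capnograph.

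**Working it through.** **Inputs.** Table 12: mainstream n = 37, mean 14, SD 2.62; sidestream n = 58, mean 17.87, SD 2.64. Results text and Table 11: pooled lead 16.36 s, SD 3.23, SEM 0.332, 95% CI 15.70 to 17.02; mean times 26.79 and 43.03 s. The printed differences are positive, so they are read as the time by which ultrasonography came first.

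**1. Do the Table 12 rows reproduce the pooled figures?**
- Mean: (37 × 14 + 58 × 17.87)/95 = 1554.46/95 = 16.36 s.
- Within-subgroup sum of squares: 36 × 2.62² + 57 × 2.64² = 644.4.
- Between-subgroup sum of squares: 37 × (14 − 16.363)² + 58 × (17.87 − 16.363)² = 338.3.
- Total SD: √((644.4 + 338.3)/94) = 3.23 s.
- SEM: 3.23/√95 = 0.331 s (printed 0.332). The t interval on 94 df is 15.70 to 17.02 s.

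The rows are consistent with the pooled lead. Back-solving the mainstream mean gives (95 × 16.36 − 58 × 17.87)/37 = 13.99, so the printed 14 is not a coarse rounding.

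**2. What do the printed p-values test?** Paired tests within each row:
- mainstream: t = 14/(2.62/√37) = 32.5; 95% CI 13.13 to 14.87 s;
- sidestream: t = 17.87/(2.64/√58) = 51.6; 95% CI 17.18 to 18.56 s.

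Both agree with p < 0.01, so the p-values in Table 12 fit ultrasonography versus capnography within each subgroup.

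**3. The between-subgroup contrast.**
- Difference in lead: 17.87 − 14 = 3.87 s.
- Pooled SD: √(644.4/93) = 2.632; SE: 2.632 × √(1/37 + 1/58) = 0.554.
- t = 3.87/0.554 = 6.99 on 93 df; p about 4e-10; 95% CI 2.77 to 4.97 s.
- Welch: t = 7.00 on 77.3 df, with the same CI to two decimals.

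The pooled interval (15.70 to 17.02) overlaps neither subgroup interval.

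**4. An unresolved mismatch.** Table 11's own means give 43.03 − 26.79 = 16.24 s, not 16.36 s. Suppose 16.24 were right and the whole error lay in one row of Table 12:
- error in the mainstream row: mean (95 × 16.24 − 58 × 17.87)/37 = 13.68, contrast 4.19 s;
- error in the sidestream row: mean (95 × 16.24 − 37 × 14)/58 = 17.67, contrast 3.67 s.

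Both values lie inside 2.77 to 4.97 s. The mismatch does not remove the contrast, but it is a reason to take final figures from patient data.

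**5. What device type is mixed with.** Under Materials and Methods, mainstream devices were used only in TUTH operating rooms 1 and 2; TUTH room 7 and the MCVTC rooms had sidestream devices. All 31 MCVTC patients are therefore sidestream, leaving 58 − 31 = 27 sidestream patients at TUTH, and 37 + 27 = 64 matches the TUTH total. Device is fully aligned with operating room and partly with centre.

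**The case against.** The stated question was only whether sidestream delay affected the significance of the time difference, and the mainstream subgroup alone answers it: with no expected delay, the lead is still 14 s. That stands.

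The device effect is also not hidden. Table 12 prints both leads, so the contrast is one subtraction. The Discussion gives both lead ranges, an expected delay of 2 to 4 s, and an 8.5 s difference in median capnography time. It attributes the larger lead to sidestream devices. The layout of Table 12 lets a careful reader see what was tested. All this stands too. It leaves missing the contrast in lead with its interval, any statement that device is confounded with room, and wording that matches the tests. The 8.5 s figure is no substitute, because it includes intubation time, as the Discussion acknowledges. The paired lead removes that, since both times run from the same start.

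Several stronger readings are tempting but unsupported:
- A reader might infer that non-normality invalidates the t-tests. With t of 32.5 and 51.6, and means close to medians (14 and 14; 17.87 and 17.50), direction and significance do not depend on it.
- A reader might infer that 16.36 s is wrong. It is a correct average of a mixed sample and lies inside both subgroup ranges (9 to 19 s; 12 to 24 s).
- A reader might infer that the device caused the 3.87 s, or that operators differed by device. Room is inseparable from device, and the documents say only that several people operated ultrasound.
- A reader might infer that most of the lead comes from waiting for six breaths. First-breath time was not recorded. Six cycles at 26 per minute take 6 × 60/26 = 13.85 s, more than the smallest lead of 9 s, so the share cannot be determined.

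**Conclusion.** The point holds as a reporting error with a limited but real consequence. The normality sentence contradicts its own p-value, and the documents do not show which part is the slip. The test described as between-subgroup is reported only as two within-subgroup p-values. That ultrasonography was significantly faster with either capnograph type is supported. That device type left the size of the lead unchanged is not: the printed summaries give a sidestream lead 3.87 s longer (95% CI 2.77 to 4.97), which is 3.87/16.36 = 24% of the pooled lead. The 16.36 s figure thus depends on the 37:58 mix.

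This rests on the Table 12 means and SDs being right and on the rows being independent groups of patients. It describes a difference between subgroups, not an isolated effect of the device.

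**What to change.** 1. Correct the Shapiro-Wilk sentence or its p-value after checking the output.
2. Label the Table 12 p-values as within-subgroup paired tests of ultrasonography versus capnography.
3. Report the between-subgroup contrast in lead with its 95% CI, recalculated from patient data (about 3.87 s, 2.77 to 4.97, from the printed summaries), and resolve 16.24 versus 16.36 s in Table 11 at the same time. Describe the contrast as not listed in the Statistical Analysis section and as confounded with operating room and partly with centre. Operator differences by device may be mentioned as possible but undocumented.
4. In the subgroup paragraph and the Discussion, say that ultrasonography was earlier in both subgroups but that its lead was about 3.9 s longer with sidestream. Give 14 s and 17.87 s beside 16.36 s.

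The cost is one short re-analysis of existing data and a few reworded sentences. No new data are needed, and the direction and significance of the time result do not change. A contrast restricted to TUTH is not required, because device and room would still coincide there.
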